### 3 OBJECTIVES AND ENDPOINTS

Objectives & Endpoints:	Objectives	Endpoints
Primary	1. Phase 0: To measure the pharmacokinetic (PK) effects of infigratinib in recurrent high-grade glioma participants.	1. Phase 0: Total and Unbound infigratinib concentration in enhancing and non-enhancing tumor tissue (8hr), plasma (0-24H) and CSF (8hr) will be determined.
	2. Expansion Cohort: Examine progression-free survival in recurrent high-grade glioma participants with demonstrated PK effects	2. Expansion Cohort: 6-month Progression-free survival (PFS6) rate from time of surgery to date of recurrence
Secondary	1. Phase 0: PD Analysis	1. Phase 0: percentage of pERK+, MIB-1+ and Cleaved Caspase 3+ cells from the surgical tissue will be quantified and compared to baseline archival/biopsy tissue.
	2. Expansion cohort: To monitor safety and tolerability of study drug combinations in participants with recurrent high-grade glioma.	2. Expansion Cohort: Safety and tolerability: 
 
a. Drug-related toxicity
 
b. Number of Adverse Events through study completion, assessed up to 60 months
 
c. Treatment-emergent adverse events (TEAEs)
 
d. Deaths
 
e. Clinical laboratory abnormalities per CTCAE (Version 5.0)
 

Exploratory	1. Phase 0: Describe systemic PK	1. Phase 0: Systemic plasma PK profile parameters ( $T_{max}$ , $C_{max}$ , $t_{1/2}$ , $AUC_{0-24h}$ ) for total and unbound levels will be determined for infigratinib.
	2. Expansion cohort: Examine Overall Survival (OS) in recurrent high-grade glioma participants with demonstrated PK effects	2. Median Overall Survival (OS) from time of surgery to date of death from any cause

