### 4.3 JUSTIFICATION FOR DOSE

#### 4.3.1 DOSE RATIONALE FOR INFIGRATINIB

#### 4.1 END OF STUDY DEFINITION

A participant is considered to have completed the study if he or she has completed Phase 0 of the study including the Phone Follow Up visit shown in the Schedule of Activities (SoA), Section 1.2. All participants will be followed for survival. Participants will be followed until death for up to 5 years following the last dose administration.

The end of the study is defined as completion of the last visit or procedure shown in the SoA in the trial by the last participant enrolled across all sites.

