**Progressive Disease (PD)**

Defined by any of the following:  $\geq 25\%$  increase in the sum of the products of perpendicular diameters of enhancing lesions compared with the smallest tumor measurement obtained either at baseline (if no decrease) or best response on stable or increasing doses of corticosteroids†; significant increase in T2/FLAIR nonenhancing lesion on stable or increasing doses of corticosteroids compared with baseline scan or best response after initiation of therapy† not caused by comorbid events (e.g., radiation therapy, demyelination, ischemic injury, infection, seizures, postoperative changes or other treatment effects); any new lesion; clear clinical deterioration not attributable to other causes apart from the tumor (e.g., seizures, medication adverse effects, complications of therapy, cerebrovascular events, infection, etc.) or changes in corticosteroid dose; failure to return for evaluation as a result of death or deteriorating condition; or clear progression of nonmeasurable disease.

---

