### 9.4 STATISTICAL ANALYSES

#### 9.4.1 ANALYSIS OF THE PRIMARY EFFICACY ENDPOINT(S)

Phase 0 endpoint PK Analysis:

A positive PK response will be unbound concentrations of infigratinib (along with its active metabolites) reaching 5-fold higher than their respective cell-free biochemical IC50 values within the non-enhancing region of the tumor.

Expansion cohort endpoint: For the primary endpoint of PFS rate at 6 months:

- Progression-free survival (PFS) is defined as the number of days from the date of surgery to the first documentation of progression or death due to any cause. Participants who remain alive without progression will be censored for PFS at the date of their last tumor assessment.

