## A Phase 0 Study of Infigratinib in Recurrent Glioblastoma Patients Protocol 2020-08

Participants removed from study treatment due to symptomatic deterioration will be considered as having progression for the purposes of the primary endpoint.

- Disease progression is defined per RANO criteria for high-grade glioma patients.

---

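### PFS6 credits a participant whose scans stop before month 6 without deterioration if death follows after month 6, but censors the same participant if alive

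*Combined protocol and SAP*

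**What the plan says.** The Expansion Cohort's primary endpoint in Section 3 is the "6-month Progression-free survival (PFS6) rate from time of surgery to date of recurrence". Section 9.4.1 measures PFS "from the date of surgery to the first documentation of progression or death due to any cause". Its only censoring sentence is: "Participants who remain alive without progression will be censored for PFS at the date of their last tumor assessment". It sets no limit on the time between the last scan and a death.

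Two further lines in 9.4.1 bear on missed scans:
- One covers stopping drug because of worsening symptoms: "Participants removed from study treatment due to symptomatic deterioration will be considered as having progression for the purposes of the primary endpoint".
- The other ties the event to a response standard: "Disease progression is defined per RANO criteria for high-grade glioma patients". The RANO definition of progression in Section 8.1.4.1 includes "failure to return for evaluation as a result of death or deteriorating condition".

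The Schedule of Activities (Section 1.2) has MRI every 3 months during the Expansion cycles and a last one at End of Study Treatment. It lists none in survival follow-up. Deaths are still collected about every 3 months by letter or phone (Section 4.1.2), and the End of Study Definition says: "Participants will be followed until death for up to 5 years following the last dose administration".

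Section 9.4.5 rules out imputing missing efficacy data, and Section 9.1 says there will be no separate SAP. Kaplan-Meier is named for overall survival (Section 9.4.6), but no estimator is named for PFS6.

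**The concern.** Scheduled scans end with treatment, while deaths are recorded for years afterwards. Stopping treatment without progression is foreseeable, because Table 3 in Section 6.1.3 contains many toxicity-driven discontinuations.

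Take two participants who stop for toxicity at month 2 with a clean scan and are not scanned again. One is alive at data cut-off and is censored at month 2. The other dies at month 9, so PFS is 9 months and the participant counts as progression-free at month 6. Their tumor data are identical. The later death turns an unknown month-6 status into a success.

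The error goes in one direction, upward. The estimate can also rise as deaths accrue after month 6, with no new tumor information. In a cohort of about 10, one or two such cases visibly change the reported rate.

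**Working it through.** **Plan's own figure.** Section 9.2: 400 operations per year × 5% × 50% = 10 enrolled per year. Over 24 months that is 20, and 50% of 20 gives about 10 in the Expansion Cohort. The 20 is reproduced. No PFS6 target, power or test is stated, so there is nothing further to reproduce.

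**Landmark.** Section 9.4.5 uses 30.4375 days per month: 6 × 30.4375 = 182.6 days.

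**When the credit arises.** Take a participant with no documented progression whose last clean scan was before month 6.

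| Later course | Result under the plan |
|---|---|
| Gap due to deteriorating condition, or removed for symptomatic deterioration | Progression (8.1.4.1, 9.4.1) |
| Other reason, death by day 182 | Event before the landmark: failure |
| Other reason, alive at cut-off | Censored at last scan |
| Other reason, death from about day 183 | Dated at death: credited at 6 months |

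Only the last row is the problem.

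**Cohort of 10 (illustrative).** Assumptions: Kaplan-Meier at day 182.6; 5 documented failures (2 at month 3.2, 3 at month 5.5); k participants with a last scan at month 1 or 3 and death at month 9; the other 5 − k progression-free past month 6.
- As written, all 10 are at risk and 5 fail: 5/10 = 50% for any k.
- Censored at the last scan, the k leave before the first failure: (5 − k)/(10 − k).
- Counted as failures at the next scheduled scan (month 3 or 6): (5 − k)/10.

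| k | As written | Censored | Failure |
|---|---|---|---|
| 1 | 50% | 4/9 = 44.4% | 40% |
| 2 | 50% | 3/8 = 37.5% | 30% |
| 3 | 50% | 2/7 = 28.6% | 20% |

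If these deaths fall at month 5 instead, the plan as written gives 40%, 30% and 20%, and no credit arises.

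**Expected bias (simulation, 400,000 participants per scenario).** All rates are assumptions: exponential PFS with median 2, 3 or 4 months; exponential time from progression to death with median 6 months; 10%, 20% or 30% stopping without progression by month 6; no scan after stopping; last scan at the stop date. True PFS6 is 0.5^(6/median): 12.5%, 25% and 35.4%.

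With 30 months of follow-up for everyone, PFS6 as written is:

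| PFS median | True | 10% stop | 20% stop | 30% stop |
|---|---|---|---|---|
| 2 months | 12.5% | 14.6% | 16.7% | 19.1% |
| 3 months | 25% | 27.1% | 29.2% | 31.3% |
| 4 months | 35.4% | 37.2% | 39.3% | 41.2% |

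The smallest difference is 37.2 − 35.4 = 1.8 points and the largest is 19.1 − 12.5 = 6.6, so about +2 to +7. Section 9.2 implies 24 months of accrual plus 6 of follow-up. With uniform accrual, follow-up runs from 6 to 30 months and the bias is about +1 to +4.5 points. If half of the stoppers' progressions are captured by other scans, it falls to about +0.4 to +2.2. Censoring the post-month-6 gap deaths at the last scan leaves a bias of about −0.2 to −1.4 points.

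**The case against.** The strongest reply is that dating death as a PFS event is a common convention, and that other text already covers the usual case. In recurrent glioma, people who miss scans and then die have often deteriorated. Sections 9.4.1 and 8.1.4.1 make that progression, although neither gives the event date. This stands. It limits the point to gaps with other causes.

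The absence of later scans is also not certain. Section 7.1 says remaining study procedures continue after treatment stops, and note 9 to the Schedule of Activities makes MRI routine care. Off-treatment scanning is therefore ambiguous rather than excluded. This stands too and lowers the expected bias.

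A reader might infer that any death after a scan gap is credited. It is not: a death by month 6 is a failure. Nor is every credit wrong. In the 30-month simulation about 40–66% of those credited had progressed before month 6, so the rest were credited correctly. A reader might also take +2 to +7 points, or 10 points per participant, as the trial's bias. The first needs 30 months of follow-up for all and no later scans. The second is the contrast with counting a failure; against censoring, one case is worth 50 − 44.4 = 5.6 points.

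Finally, PFS6 is descriptive (Section 9.1), so no error rate or power changes. With 10 participants its standard error is about 10–15 points (√(0.125 × 0.875/10) = 10.5; √(0.354 × 0.646/10) = 15.1), larger than the expected bias. That limits the weight of the point but does not justify treating identical tumor data differently according to later death.

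**Conclusion.** The point holds in limited form. As written, 9.4.1 gives an upward-biased PFS6 whenever scans stop before month 6 for a reason other than deterioration and death follows after about day 183. This comes from the stated rule; it is not merely missing detail.

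The expected bias is about +1 to +4.5 points with 6–30 months of follow-up and +2 to +7 with 30 months for all. It is smaller if routine-care scans capture progression. These ranges rest on assumed progression, stopping and death rates and on Kaplan-Meier, none of which the documents give for PFS6. The cohort-of-10 figures show sensitivity and are not a forecast. The documents do not support a claim that deaths in general inflate PFS6, or that counting death as a PFS event is itself an error. The change should be made because PFS6 is the cohort's primary endpoint and the choice is best fixed before results are seen.

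**What to change.** Amend Section 9.4.1 to state:

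- PFS6 is the Kaplan-Meier estimate at 6 months from surgery.
- A participant who dies after month 6, and whose last adequate tumor assessment without progression was before the month-6 scan window, is censored at that assessment, as a living participant would be. The window should admit a scan shortly before day 183, so that one at day 180, for example, qualifies.
- Death by month 6 remains an event.
- One sensitivity analysis counts such participants as failures at the next scheduled scan, dated no later than month 6 so that they count at the landmark.

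State this together with the rule for living participants who miss scans, since both belong to the same missing rule. Overall survival is unchanged.

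The cost is a few sentences and one extra analysis line, with no new data. PFS6 becomes slightly lower and its interval slightly wider. The censoring is not free of bias: keeping early deaths as events while censoring later ones removes some longer survivors from the risk set, which explains the simulated −0.2 to −1.4 points. The failure-count analysis gives the lower bound.

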## A Phase 0 Study of Infigratinib in Recurrent Glioblastoma Patients Protocol 2020-08

Participants removed from study treatment due to symptomatic deterioration will be considered as having progression for the purposes of the primary endpoint.

- Disease progression is defined per RANO criteria for high-grade glioma patients.

---

### 9.4.2 ANALYSIS OF THE SECONDARY ENDPOINT(S)

PD Analysis: To compare pharmacodynamics biomarkers, paired archival, biopsy (if available) and surgical tissue will be examined. Once the percentage of individual biomarker positive cells was quantified, a paired t test will be used to compare log-transformed percent positive cells between archival, biopsy (if available) and surgical tissue at a 2-sided 5% level.

Safety Analyses: All adverse events will be tabulated according to the highest grade observed per patient for each event or category. Tabulations (n and %) will be produced for each of the following categories: Clinical laboratory abnormalities will be coded per CTCAE (Version 5.0)

- a. All treatment-emergent Adverse Events
- b. Treatment related Adverse Events (defined as those definitely, probably, or potentially related to treatment)
- c. Serious Adverse Events

---

### 9.4.3 BASELINE DESCRIPTIVE STATISTICS

Baseline characteristics, including demographics and laboratory measurements, will be summarized using descriptive statistics. Mean, Median, Minimum and Maximum values will be reported for continuous values such as age and laboratory values, and N and % will be reported for categorical values such as sex and performance status.

---

### 9.4.4 PLANNED INTERIM ANALYSES

No planned interim analysis will be carried out.

---

### 9.4.5 DATA HANDLING RULES

#### **Conversions from Days to Years, Months or Weeks**

Years = # of days / 365.25

Months = # of days / 30.4375 (i.e. 365.25/12)

Weeks = # of days / 7

Values based on the above computations will be rounded to tenths.

#### **Computation of Duration**

Duration for time variables based on two dates, e.g., Start Date and End Date, will be calculated as (End Date – Start Date + 1) (in days) unless otherwise specified.

#### **Missing normal ranges for laboratory parameters**

When either the lower limit of normal, the upper limit of normal or both are missing or are not machine readable, a standardized reference range will be used.

#### **Non-Numeric Laboratory Results and Calculation of Normal Ranges**

A Phase 0 Study of Infigratinib in Recurrent Glioblastoma Patients  
Protocol 2020-08

Laboratory values including symbols (“<” or “>”, for example) will not be used in summary analyses. These values will be reflected in listings of the data. When there are potential conflicts between local lab normal ranges and ranges used in CTC grading, CTC normal ranges will be used.

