## 8 STUDY ASSESSMENTS AND PROCEDURES

### 8.1 EFFICACY ASSESSMENTS

#### 8.1.1 PHARMACOKINETIC (PK) MEASUREMENTS

The total and unbound concentrations of infigratinib in plasma, CSF, and tumor tissues (including contrast-enhancing and non-enhancing regions) will be determined by a validated LC-MS/MS method. All analyses will be performed at the Ivy Brain Tumor Center.

See the Ivy Brain Tumor Center Laboratory Manual for details regarding collection, processing, packaging and shipment.

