### 8.2.12 LABORATORY EVALUATIONS

Blood will be obtained and sent to the local laboratory for a CBC/hematology, blood chemistry, and pregnancy test as noted in the below table.

Table 9 Clinical laboratory parameters collection plan

Test Name	Test Category
Hematology	Hgb, platelets, white blood cells (WBC), red blood cells (RBC), differential (basophils, eosinophils, lymphocytes, monocytes, neutrophils [% or absolute])
Blood Chemistry	Albumin, amylase (or lipase), ALT, AST, bicarbonate, calcium, chloride, creatinine, total bilirubin, direct bilirubin (only if total bilirubin is ≥ grade 2), blood urea nitrogen (BUN), potassium, sodium, random or fasting glucose, alkaline phosphatase, total protein, magnesium, phosphorus Calculated or measured creatinine clearance
Urinalysis	Macroscopic panel (dipstick) (bilirubin, blood, glucose, ketones, WBC, pH, protein, specific gravity) Reflexive Microscopic panel (RBC, WBC, casts)
Pregnancy test	At screening visit, serum pregnancy test At subsequent cycles, urinary pregnancy test.
Coagulation	International normalized ratio (INR) and pro-thrombin time (PT) or Quick Test; activated partial thromboplastin time (PTT)

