### 8.3 ADVERSE EVENTS AND SERIOUS ADVERSE EVENTS

### 8.3.1 DEFINITION OF ADVERSE EVENTS (AE)

Adverse event means any untoward medical occurrence associated with the use of an intervention in humans, whether or not considered intervention-related (21 CFR 312.32 (a)). Adverse Events that are will be captured following first administration of study drug.

AEs include:

- Any deleterious change from the participant's baseline status, including an increase in the severity or frequency of a pre-existing abnormality or disorder;
- Concurrent illnesses;
- Injury or accidents;
- Subjective symptoms considered unfavorable by the reporter;
- Clinically significant physical examination, laboratory, imaging, or physiological testing abnormalities (abnormalities requiring treatment or a change in medication are AEs)
- Overdose

AEs do not include:

- Laboratory or test abnormalities that are not considered clinically significant
- Incidental findings on imaging that are not considered clinically significant
- Conditions for which a procedure was planned prior to signing the informed consent (e.g., elective knee replacement)
- Conditions present at baseline which have not worsened
- Hospitalization solely to complete procedures, or for social reasons such as respite care
- Cosmetic procedures
- Pregnancy without complications (see Section 8.3.9)
- Abnormal vital sign values that are not considered clinically significant; or, do not require medical intervention; or, interruption/change to study treatment; or, not accompanied by clinical symptoms.
- Events that are clearly consistent with the expected pattern of progression of the underlying disease (may be based on RANO or symptomatic deterioration).
- Events that are clearly related to surgical complications experienced as a result of the craniotomy and not related to study participation or the test article(s) should not be recorded as AEs. If there is any indication that the event may be related to study participation or the test article, the event should be recorded as an adverse event.

Cancer progression and cancer-related death are a study endpoint and will not be reported as an AE.

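### Laboratory values reported with `<` or `>` are left out of summary analyses, so a participant's most extreme result can drop out of the CTCAE laboratory endpoint

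*Combined protocol and SAP*

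**What the plan says.** The rule is in Section 9.4.5, under Non-Numeric Laboratory Results and Calculation of Normal Ranges. Laboratory values that include a symbol, with `<` and `>` as the examples, "will not be used in summary analyses. These values will be reflected in listings of the data". The same paragraph then turns to grading: "When there are potential conflicts between local lab normal ranges and ranges used in CTC grading, CTC normal ranges will be used".

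The endpoint affected is item 2e of the secondary endpoints in Section 3: "Clinical laboratory abnormalities per CTCAE (Version 5.0"). Section 9.4.2 repeats the grading system, "Clinical laboratory abnormalities will be coded per CTCAE (Version 5.0"), and gives the tabulation rule: "All adverse events will be tabulated according to the highest grade observed per patient for each event or category", as n and %. The three tabulation categories listed there are treatment-emergent, treatment-related and serious adverse events. No separate laboratory table is described.

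Safety tests are local. Section 8.2.12 says "Blood will be obtained and sent to the local laboratory", and Section 9.1 allows up to three sites. Section 8.3.1 counts as adverse events "Clinically significant physical examination, laboratory, imaging, or physiological testing abnormalities". Section 9.1 also states that there will be no separate SAP, so nothing downstream is planned that would refine the rule.

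**The concern.** A laboratory reports `<` or `>` when a result lies beyond the range it can report, so these are by construction the lowest and highest values. For grading they are usually informative, because the limit itself fixes a minimum grade. A rule that sets them aside removes data because they are extreme.

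At stake is the completeness of endpoint 2e. If a participant's worst value is symbol-coded, the participant is shown at a lower grade or disappears from the laboratory table. If reporting limits differ between local laboratories, the same true value could be counted at one site and dropped at another.

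The sentence on normal ranges raises a second, smaller issue. The protocol does not define CTC normal ranges. Section 5.1 uses the institutional ULN for AST, ALT and amylase or lipase, and Table 3 gives multiples of ULN without naming a source. One value could therefore receive two grades.

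**Working it through.** **Inputs.** From Section 9.2: 400 operations per year, 5% carrying the alteration, 50% capture, 24 months of accrual, and 50% of Phase 0 entering expansion. From Section 9.4.5: the exclusion rule. From Table 3: grade boundaries for platelets and for amylase/lipase. The protocol does not give reporting limits or the number of symbol-coded results, so those are assumed.

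**1. The plan's own numbers.** 400 × 0.05 = 20 eligible per year; 20 × 0.50 = 10 enrolled per year; 10 × 2 years = 20 in Phase 0, as stated. Expansion: 20 × 0.50 = 10.

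**2. Is the grade known from the limit?** Table 3 puts Grade 4 platelets below 25 × 10⁹/L. A result of `<10` is therefore Grade 4 with certainty. Table 3 puts asymptomatic amylase or lipase at Grade 3 above 2.0 and up to 5.0 × ULN, and at Grade 4 above 5.0 × ULN. A result above a ceiling of at least 5.0 × ULN is Grade 4; a result above a ceiling between 2.0 and 5.0 × ULN is at least Grade 3. Excluding such values is not needed for grading.

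**3. Direction.** Let x of n participants truly have a high-grade abnormality, and let m of the x rest only on a symbol-coded value. The reported count is x − m, which cannot exceed x. This holds for the count only. A `<` result for ALT, AST, bilirubin, creatinine or lipase is not a high-side toxicity, and dropping it raises the mean. If a participant with no high-grade value left the denominator, the percentage would rise.

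**4. Size in the Expansion Cohort, n = 10, m = 1.**
- x = 1: 1/10 = 10% becomes 0, a loss of 10 percentage points.
- x = 2, participant stays in the denominator at a lower grade: 2/10 = 20% becomes 1/10 = 10%, again 10 points.
- x = 2, participant leaves the denominator: 1/9 = 11.1%, a loss of 8.9 points.

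One lost value therefore costs at most 1/10, or 10 points.

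**5. Size if all 20 participants were tabulated (upper bound on n), x = 4, true rate 20%.**

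| Symbol-coded among the 4 | Leaves denominator | Stays in denominator |
|---|---|---|
| 1 | 3/19 = 15.8% | 3/20 = 15% |
| 2 | 2/18 = 11.1% | 2/20 = 10% |
| 4 | 0/16 = 0% | 0/20 = 0% |

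The values of x and m are assumptions chosen to show the range.

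**The case against.** **The adverse-event route.** The highest-grade tabulation in Section 9.4.2 is of adverse events, which the investigator records. Section 8.3.1 includes clinically significant laboratory abnormalities and those that need treatment or a change of medication. Table 3 calls for a hold or discontinuation at Grade 3 or 4 for neutrophils, platelets, lipase, transaminases and others. A platelet count of `<10` should therefore reach the AE tables whatever Section 9.4.5 says. This stands, and it confines the loss to endpoint 2e and the laboratory summaries. It does not remove it: the AE route filters on clinical significance, while endpoint 2e is defined by CTCAE grade alone. A reader might infer that the plan understates severe toxicity throughout; the documents do not support that.

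**The meaning of summary analyses.** The phrase could cover only means, medians and ranges, leaving coding and tabulation untouched. That reading is possible, but the text does not say so, and the next sentence of the same paragraph concerns CTC grading.

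**Drug concentrations.** A reader might infer that the rule also discards undetectable tumour concentrations and so inflates the primary PK result. For example, with 10 responders of 20 and five undetectable samples, 10/20 = 50% would become 10/15 = 67%. The documents do not support this. The heading, the neighbouring rule on missing laboratory ranges and the reference to local ranges all point to safety tests. Section 8.1.1 treats concentrations separately, saying they "will be determined by a validated LC-MS/MS method". Section 9.3 defines the PK dataset by surgery and assessment for the PK endpoint, and a sample assayed and found below quantification has, on its natural reading, been assessed. A response proportion is not an endpoint in Section 3, the 50% is an accrual estimate, and the five samples are assumed. What remains is an omission: no rule exists for concentrations below quantification, although a Day 1 pre-dose sample is scheduled.

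**Normal ranges.** The CTC ranges apply only where there is a potential conflict, so local ranges are not simply replaced. It would also go too far to say that Table 3 uses local ULN, since it says only ULN.

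**Scale.** The study is small and descriptive, and the values stay in listings that can be read line by line. This limits the harm but does not make the rule right.

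**Conclusion.** The rule in Section 9.4.5 is wrong as written for CTCAE grading. Applied literally, it can lower but never raise the count of high-grade abnormalities under endpoint 2e. One lost value moves the rate by up to 10 percentage points with about 10 Expansion participants.

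That size rests on three assumptions: endpoint 2e is tabulated as participants by highest grade, the symbol-coded value is that participant's only result at that grade, and such values occur at all. The protocol gives no frequency for them. No primary endpoint is shown to change. For PK, the supported statement is only that a rule for values below quantification is missing. For normal ranges, it is that three passages need to be reconciled.

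**What to change.** In Section 9.4.5, replace the exclusion with the following.

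- A safety laboratory value reported with `<` or `>` is graded at its reporting limit, the minimum certain grade, and included in all CTCAE tabulations.
- Continuous summaries report the number of censored values, and use either the limit value or the median.
- The rule does not apply to drug concentrations. Participants with an assayed sample below quantification stay in the PK Analysis Dataset, and the number below the limit is reported. If the mean and 80% CI of Section 9.1 are kept for such data, state which value stands in for them.
- The sentence on CTC normal ranges is reconciled with the institutional ULN in Section 5.1 and the unspecified ULN in Table 3, so that one value does not receive two grades.

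The cost is a few sentences and no new data. Reported laboratory toxicity may look slightly less favourable. Using the limit in place of the true value is a convention with some bias of its own, which is why the number censored should be shown beside it.
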